7.6.3.2 Liver histology as measured by the fibrosis stage and NAFLD Activity Score

The analysis of fibrosis stage and NAS will be performed using the LBAS and PPS. Fibrosis stage at baseline and post-baseline time points, change from baseline, and shift from baseline frequencies will be summarized by treatment group. In the calculation of change and shift from baseline, fibrosis stage 1A, 1B, and 1C will be considered as stage 1.

In addition, a descriptive summary will present the change from baseline in fibrosis at Week 24 and the change from baseline in fibrosis at week 96, irrespective of change in steatohepatitis.

NAS and components at baseline and post-baseline time points and the change from baseline frequencies together with mean (SD) and median will be summarized by treatment. Shift from baseline frequencies will be presented for the individual components of NAS as well.

7.6.3.3 Proportion of subjects who achieve improvement in liver fibrosis (\geq two stages) and no worsening of steatohepatitis at Week 24 and Week 96

A CMH test will be used to compare the differences in proportions of subjects who achieve improvement in liver fibrosis (\geq two stages) and no worsening of steatohepatitis at Week 24 and Week 96 between the EFX arms and the placebo arm, adjusting for stratification factors. The analysis will be performed using the LBAS. The point estimates and 95% CIs for the differences in proportions, and p-values will be calculated. The 95% CI will be constructed using the Miettinen and Nurminen method. In addition, the same test will be performed to compare the difference in proportions of subjects who achieve two stage improvement in liver fibrosis at Week 24 and Week 96 between the EFX arms and the placebo arm. In addition, the odds ratio and risk ratio point estimate and 95% CI will be summarized for each EFX arm compared to placebo.

The same analysis will be repeated on the PPS for Week 24. The analysis will be repeated using the MFAS, Week 24 LBAS, and Week 96 LBAS at Week 96.

A descriptive summary will present the shift from Week 24 response to Week 96 response for the Week 24 LBAS, subjects with a Week 24 biopsy but missing Week 96 biopsy will be summarized in the missing category in this summary.

CONFIDENTIAL

Statistical Analysis Plan

Sponsor Name: Akero Therapeutics, Inc.
Sponsor Protocol ID: AK-US-001-0102

7.6.3.4 Clinical outcomes of event-free survival

EFS will be assessed by time to the first clinical event including progression to cirrhosis as determined by central pathology, adjudicated liver decompensation events, liver transplantation and all-cause mortality using the FAS. For subjects without any clinical event at the analysis cutoff date, EFS will be censored on the date of last assessment. The number and percentage of subjects with clinical event and subjects censored at the time of analysis will be presented. The 50th percentile of Kaplan-Meier estimates will be used to estimate the median duration of EFS (months). A two-sided 95% CI will be provided for this estimate. The 25th and 75th percentiles, and the range (minimum, maximum) will be presented as well. The range will be determined including censored observations.

In the event that the median EFS is not reached, the pointwise confidence interval for the survival probability at clinically relevant timepoints may be presented.

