This is a Phase 2b, randomized, double-blind, placebo-controlled study evaluating the safety and efficacy of EFX in non-cirrhotic subjects with NASH. Subjects will be fibrosis stage 2 or 3 (F2-3) and dosed weekly with EFX or placebo. Following the 24-Week analysis, selection of the 28 mg or 50 mg EFX dose will be based on achieving the efficacy endpoints and in consideration of the safety and exploratory analysis. Subjects will be followed for long-term safety until Week 96.

The dose and length of administration of the drug in AK-US-001-0102 are supported by safety data from nonclinical studies and from the safety and efficacy data from the Phase 2a study.

NASH with fibrosis is a condition with a high risk of progression to cirrhosis which may lead to end-stage liver disease and increase the risk of HCC. Thus, reversing the fibrotic process in addition to ameliorating the metabolic dysfunction that drives NASH pathogenesis is paramount to improving the prognosis of this condition. The current gold standard for assessing fibrosis is liver biopsy. As such, improvement in liver fibrosis without worsening of NASH as assessed by liver biopsy will be evaluated as the primary efficacy parameter in this Phase 2b study. Efficacy will be determined by changes in liver histology. In addition, effect of EFX on clinical outcome events will be evaluated based on adjudicated hepatic clinical event rates that include hepatic decompensation, liver transplantation, and all-cause mortality. Due to the increased risk of cardiovascular morbidity and mortality in NASH ([Angulo et al. 2015](#), [Ekstedt et al. 2015](#), [Targher et al. 2016](#)), the impact of EFX on metabolic parameters (e.g., lipids and insulin resistance) will be monitored and cardiovascular events will be prospectively recorded and adjudicated.

However, liver biopsy has numerous limitations including its invasiveness and the potential for serious complications, which deter many patients from seeking evaluation for NAFLD or enrolling in clinical trials of novel therapies. Liver biopsy is also limited by cost, sampling error, and variability in histopathological interpretation. Due to these limitations, the

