6.25.1. Hepatic Events Adjudication Committee

A key objective of this study is to prevent progression to cirrhosis and associated complications. Clinical events that constitute the clinical outcomes endpoint include:

- 1) Progression to cirrhosis as defined by a liver biopsy showing F4 fibrosis according to the NASH CRN classification, as assessed by the central reader.
- 2) Events of hepatic decompensation including:

- a) Clinically apparent ascites requiring treatment
- b) HE of Grade 2 or above (according to the West Haven criteria defined in [Appendix E](#)) requiring treatment
- c) Portal hypertension-related upper gastrointestinal bleeding identified by endoscopy and requiring hospitalization, including events of bleeding from esophageal varices, gastric varices, and portal hypertensive gastropathy
- 3) Liver transplantation or qualification for liver transplantation, defined as MELD score ≥ 15 (unless due to therapeutic anticoagulation) on at least 2 consecutive occasions at least 4 weeks apart
- 4) All-cause mortality

Each of the clinical events (except histologic progression to cirrhosis, all-cause mortality and liver transplantation) will require confirmation by a Hepatic Events Adjudication Committee. All deaths will be reviewed by this committee to determine if they are liver-related.

If there is clinical evidence that a subject has progressed to cirrhosis (e.g., based on the presence of new esophageal varices, changes in biomarkers [including, but not limited to, low serum albumin, high serum bilirubin, a low platelet count, prolonged INR, or elevated liver stiffness], or development of other clinical signs or symptoms of cirrhosis), the subject should undergo repeat liver biopsy for confirmation of progression to cirrhosis (F4 fibrosis as assessed by the central reader according to the NASH CRN classification) at the discretion of the principal investigator (PI).

Once the clinical event (except histological progression to cirrhosis, all-cause mortality and liver transplantation) is confirmed by the Hepatic Events Adjudication Committee, the subject will discontinue from the study. Subjects who experience histological progression to cirrhosis, all-cause mortality and liver transplantation will be discontinued from the study, but do not require confirmation from the adjudication committee prior to discontinuation.

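### The SAP's event-free survival list leaves out transplant qualification (MELD ≥15), a protocol outcome event; coded as printed, it would be censored instead of counted

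*SAP*

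**What the plan says.** Protocol section 6.25.1 sets out the outcome composite under the words "Clinical events that constitute the clinical outcomes endpoint include". It has four items: F4 on biopsy by the central reader; hepatic decompensation (ascites, encephalopathy, portal-hypertensive bleeding); "Liver transplantation or qualification for liver transplantation, defined as MELD score" of at least 15 on at least two consecutive occasions at least four weeks apart, unless due to therapeutic anticoagulation; and death from any cause.

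The same section exempts only histological progression, death and transplantation from adjudication. MELD qualification is not among the exemptions. Once an adjudicated event "is confirmed by the Hepatic Events Adjudication Committee, the subject will discontinue from the study".

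SAP section 7.6.3.4 defines the analysis: "EFS will be assessed by time to the first clinical event including progression to cirrhosis as determined by central pathology", followed by "adjudicated liver decompensation events, liver transplantation and all-cause mortality using the FAS". Its censoring rule is: "For subjects without any clinical event at the analysis cutoff date, EFS will be censored on the date of last assessment".

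**The concern.** The SAP follows the protocol's list item by item but stops halfway through the third: transplantation is named and qualification for it is not. A programmer working from SAP 7.6.3.4 alone would have no code for a confirmed MELD event. The subject would then be treated as event-free and censored at the last assessment.

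Kaplan-Meier estimation assumes that subjects censored at a given time have the same future risk as those still followed. Here the subject leaves the study because liver function has deteriorated, so the censoring is informative and the event-free estimate for that arm is too high. The trial enrols non-cirrhotic F2-F3 subjects, so few outcome events are likely and each one coded differently would be visible.

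**Working it through.** **Step 1. Components side by side.**

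| Component | Protocol 6.25.1 | SAP 7.6.3.4 |
|---|---|---|
| F4 by central pathology | yes | yes |
| Hepatic decompensation | yes, adjudicated | yes, adjudicated |
| Liver transplantation | yes | yes |
| Qualification for transplantation (MELD ≥15, confirmed) | yes | not named |
| All-cause mortality | yes | yes |

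**Step 2. Can another SAP component absorb it?** Not decompensation. Protocol 6.25.1 lists that as a separate item with its own three criteria, and Protocol Table 6 also has separate entries for MELD ≥15 and for a decompensation event. In Table 6, MELD ≥15 makes the subject a non-responder for the primary endpoint, so there it is treated as a failure.

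**Step 3. Does the subject leave the study?** Yes. MELD qualification needs adjudication, and confirmation discontinues the subject. If transplant qualification were read as sharing the transplantation exemption, the subject would still be discontinued, only without adjudication first.

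**Step 4. Is the difference declared?** SAP section 8 states that changes to the planned analysis are not applicable and notes only that the switch to a single EFX dose did not take place.

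**Step 5. Scale.** The visible text gives no EFS event rate, event count or hazard ratio, so there is no plan figure to reproduce. The following is an illustration on assumed inputs:
- n = 40 per arm (Protocol 5.2.2).
- k = 0 to 4 other events, spread evenly over 96 weeks (assumed).
- m = 1 to 3 subjects whose first event is MELD qualification just after Week 48 (assumed).
- No other censoring (assumed).

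The Week 96 estimate is the product over event times of (1 − 1/r), where r is the number at risk. If the MELD subjects are counted, this reduces to (40 − k − m)/40. If they are censored, they leave the risk set without contributing a factor.

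Worked case, k = 2 (Weeks 32 and 64), m = 1:
- Counted: 37/40 = 92.5%.
- Censored: (39/40) × (37/38) = 0.975 × 0.9737 = 94.9%.
- Difference: 2.4 points.

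| k | m | Counted | Censored | Difference (points) |
|---|---|---|---|---|
| 0 | 1 | 97.5% | 100.0% | 2.5 |
| 2 | 1 | 92.5% | 94.9% | 2.4 |
| 4 | 1 | 87.5% | 89.9% | 2.4 |
| 0 | 2 | 95.0% | 100.0% | 5.0 |
| 4 | 2 | 85.0% | 89.7% | 4.7 |
| 0 | 3 | 92.5% | 100.0% | 7.5 |
| 4 | 3 | 82.5% | 89.6% | 7.1 |

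**The case against.** The strongest reply is that the SAP does not exclude the event. Its list opens with *including*, and the censoring rule speaks of any clinical event, not any listed event. *Clinical event* is also the protocol's term for the 6.25.1 components. SAP 3.3, where exploratory endpoints are defined, is blacked out and may hold the full definition. Protocol section 1.6 uses a similar shorthand, "adjudicated hepatic clinical event rates that include hepatic decompensation, liver transplantation, and all-cause mortality", which omits both MELD qualification and F4, and nobody would conclude from it that F4 had been removed.

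Much of this stands. A reader might infer that the SAP deliberately removed the event or that censoring is required. The documents support neither. What remains is that a time-to-event endpoint needs a closed list of events, and the only visible operative text leaves one protocol component to interpretation. The section 1.6 wording is a rationale summary, not an analysis rule.

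The affected group is also narrow:
- Only subjects whose first event is MELD qualification are at issue.
- F4 on biopsy would still count. Protocol 6.25.1 allows a repeat biopsy at the investigator's discretion, and Appendix B allows one for adjudication, or at early termination if the last was at least 12 months earlier.
- Entry limits on INR, bilirubin and platelets, and the exclusion of cirrhosis, make such a first event unlikely within 96 weeks.

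A reader might also infer that later transplant or death could never be observed. That is too strong: there is a 30-day follow-up visit, and Protocol 6.19 provides for vital-status searches to limit loss to follow-up. The supportable statement is that participation ends after that visit (Protocol 3.3), so later events are not systematically captured.

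Finally, a reader might assume two to four events per arm and say that recoding one lowers the count by 25% to 50% (1/4 or 1/2). That is arithmetic on an assumption. The documents give no event rate and do not show that any such event would occur.

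**Conclusion.** The mismatch between SAP 7.6.3.4 and Protocol 6.25.1 is real and undeclared in the visible text. Its consequence is conditional. If the list is programmed as printed, a subject whose first event is MELD qualification without F4 becomes an informative censoring, and that arm's EFS estimate is biased upward. Under the stated assumptions the shift is about 2.4 to 2.5 points at Week 96 per such subject in an arm of 40. If no such subject occurs, the shift is zero.

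EFS is exploratory, and 7.6.3.4 specifies only event counts and Kaplan-Meier summaries, with no between-arm test or hazard ratio. The direction of any bias between arms depends on where the events fall and cannot be stated in advance. The matter is worth correcting because it is cheap and removes an ambiguity in how a protocol-defined failure is coded.

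**What to change.** In SAP 7.6.3.4, replace the open list with a closed one identical to Protocol 6.25.1, adding adjudicated qualification for liver transplantation (MELD ≥15 as defined there) as an event. State the event date, either the first or the confirming MELD value. The two are at least four weeks apart, and the visible text gives no dating rule. If SAP 3.3 already carries the full definition, a cross-reference would settle the component list.

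If the omission is intended, declare and justify it in SAP section 8 and add a sensitivity analysis that counts the event.

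The cost is one phrase and a dating rule. No new data are needed: MELD is already an analysis variable (SAP 7.6.3.9) and the event already goes to adjudication.

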Eligible subjects will be randomized to one of three treatment groups with a ratio of 1:1:1

Group A: Placebo

Group B: 28 mg EFX

Group C: 50 mg EFX

Number of Subjects Planned:

Approximately [REDACTED] subjects

Target Population:

Males and non-pregnant, non-lactating females between 18 – 75 years of age with biopsy proven F2 - F3 NASH.

Diagnosis and Main Criteria for Inclusion:

Inclusion Criteria

1. Males and non-pregnant, non-lactating females between 18 - 75 years of age inclusive, at the time of the screening visit.
2. Previous history or presence of 2 out of 4 components of metabolic syndrome (obesity, dyslipidemia, elevated blood pressure, elevated fasting glucose) or type 2 diabetes.
3. **Initial Screening Visit:** After a signed informed consent and confirmation of clinical risk profile associated with NASH, a screening lab panel and elastography will be measured for all subjects during an initial screening period:
 - a. FibroScan® median liver stiffness [REDACTED]
 - b. CAP [REDACTED]

Note: All subjects must complete a FibroScan® examination during the screening period. However, the median liver stiffness and CAP inclusion criterion do not apply to subjects

with an eligible historical liver biopsy performed \leq 180 days prior to randomization which confirmed fibrosis 2-3 and a NAS \geq 4.

If a historical value for FibroScan® is available in the past 3 months prior to the Screening Visit, then the FibroScan® does not need to be repeated.

- c. AST $>$ 17 for females and $>$ 20 for males;

Note: The AST inclusion criterion does not apply to subjects with an eligible historical liver biopsy performed \leq 180 days prior to randomization which confirmed fibrosis 2-3 and a NAS \geq 4.

- d. Estimated glomerular filtration rate (eGFR) \geq 60 mL/min, as calculated by the CKD-EPI;
- e. HbA1c \leq 9.5% (or serum fructosamine \leq 381 μ mol if HbA1c is unavailable);
- f. INR \leq 1.3, unless due to therapeutic anticoagulation;
- g. Direct bilirubin \leq ULN;
- h. Total bilirubin \leq upper limit of normal (ULN), unless due to an alternate etiology such as Gilbert's syndrome or hemolytic anemia;
- i. Creatinine kinase $<$ 3 x ULN;
- j. Platelet count \geq 140,000/ μ L;
- k. Triglyceride level \leq 500 mg/dL;
- l. ALT $<$ 5 x ULN;
- m. AST $<$ 5 x ULN;
- n. ALP $<$ 2 x ULN.

Note: Subjects meeting all of the above components will move into the next screening phase.

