3.1. Overall Study Design and Plan

This is a Phase 2b, randomized, double-blind, placebo-controlled study evaluating the safety and efficacy of EFX in non-cirrhotic subjects with NASH. Subjects will be fibrosis stage 2 or 3 (F2-3) and dosed weekly with EFX or placebo.

Subjects meeting the study's eligibility criteria will be randomly assigned in a 1:1:1 ratio into 3 treatment groups as shown in Figure 2 below. Following 24 weeks of dosing, subjects will transition into the long-term safety follow-up portion of the study and will be followed until Week 96. If a subject refuses to complete the Week 24 liver biopsy, the subject will be discontinued from the study at Week 24. Only a 30-Day Follow-up visit is required following discontinuation of study drug. After all subjects have completed at least 52 weeks of treatment on their randomized dose, all subjects randomized to receive EFX will roll over into a single EFX dose arm (28 mg or 50 mg). The dose will be selected based on the Week 24 analysis and in alignment with regulatory authority.

Subjects on placebo will remain in the same treatment group for the duration of the study. After completing Week 96, subjects on placebo will be offered the option to receive EFX in a rollover study.

Figure 2. Study Schema

Randomization:

Randomization will be stratified by baseline type-2 diabetes status and fibrosis score. Study drug will be administered subcutaneously once weekly (QW). Eligible subjects will be randomized to one of three treatment groups with a ratio of 1:1:1.

- Group A: Placebo
- Group B: 28 mg EFX
- Group C: 50 mg EFX

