4.3. Exclusion Criteria

Subjects meeting any of the following criteria are not eligible for study participation:

1. Weight loss > 5% in the 3 months prior to screening until randomization or from the time of the diagnostic liver biopsy until randomization, whichever is longer.
2. Presence of cirrhosis on liver biopsy (stage 4 fibrosis).
3. Type 1 diabetes.
4. Uncontrolled Type 2 diabetes defined as:
 - a. Insulin dose adjustment >35% within 30 days prior to screening through randomization,
 - b. Symptoms of the following within 3 months prior to screening: acutely decompensated blood glucose control (e.g., thirst, polyuria, weight loss), or a history of diabetic ketoacidosis, or a history of hyperglycemic hyperosmolar state
5. Hypoglycemia unawareness, hospitalization due to hypoglycemia, or history of severe hypoglycemia (hypoglycemia requiring outside assistance to regain normal neurologic status) within 3 months prior to screening.
6. Subjects with osteoporosis, defined as a T-score of -2.5 or lower at screening.
7. Poorly controlled hypertension (systolic blood pressure > 160 mm Hg, or diastolic blood pressure > 100 mm Hg).
8. Any prior history of decompensated liver disease including ascites, hepatic encephalopathy (HE), or variceal bleeding.
9. History of pancreatitis.
Note: Subjects with a history of gallstone pancreatitis and subsequent cholecystectomy may be allowed to participate upon approval by the Medical Monitor.
10. Chronic hepatitis B virus (HBV) infection (hepatitis B surface antigen [HBsAg]) positive or acute hepatitis A infection (hepatitis A IgM antibody positive).
11. Chronic hepatitis C virus (HCV) infection (HCV antibody [Ab] and HCV ribonucleic acid [RNA] positive). Subjects cured of HCV infection < 2 years prior (based on date of RNA polymerase chain reaction [PCR] negative confirmation following conclusion of treatment) to the screening visit are not eligible.
12. Prior (< 2 years prior to screening) or planned (during the study period) bariatric surgery (e.g., gastroplasty, roux-en-Y gastric bypass). Surgery failure or reversal or removal of intragastric balloon > 2 years prior to screening would be acceptable.

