5.2.2. Dosage and Administration

Detailed information regarding the preparation and administration of EFX or placebo for this study is contained in the EFX Pharmacy Manual. Investigational medicinal product will be administered by subcutaneous injection once weekly as follows:

- Placebo QW (n = 40)
- 28 mg EFX QW (n = 40)
- 50 mg EFX QW (n = 40)

The IMP will be administered by a weekly 1.0 mL subcutaneous injection into the abdomen by a qualified staff member at the clinic or utilizing in-home nursing. The date and time of injection will be recorded. If injection site reactions are observed, mitigation procedures should be put in place as per local standard of care. Examples of mitigations include icing

the injection site, rotating the quadrant of the abdomen in which the injection is administered, or providing antihistamine prior to injection.

If subjects are unable to attend study visits and/or study centers are unable to accommodate on-site visits due to pandemics, natural disasters, or other major disruptions procedures will be put in place to allow for direct-to-subject drug shipments for utilization of in-home nursing, as necessary.

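### The event-free survival (EFS) plan leads with a median very unlikely to be informatively reached and names no EFX-versus-placebo estimate

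*SAP*

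**What the plan says.** SAP 7.6.3.4 defines the endpoint on the Full Analysis Set: "EFS will be assessed by time to the first clinical event including progression to cirrhosis as determined by central pathology", together with adjudicated decompensation, liver transplantation and death. Subjects without an event are censored at their last assessment.

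The planned outputs are:
- the number and percentage of subjects with an event and censored (SAP 7.6 makes efficacy analyses by treatment group);
- the median, described as "The 50th percentile of Kaplan-Meier estimates will be used to estimate the median duration of EFS (months"), with a two-sided 95% CI;
- the 25th and 75th percentiles and the range.

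If the median is not reached, "the pointwise confidence interval for the survival probability at clinically relevant timepoints may be presented". That output is optional and the time points are not named.

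The section mentions no test, difference, ratio or other comparison with placebo. Protocol 1.6 says the "effect of EFX on clinical outcome events will be evaluated based on adjudicated hepatic clinical event rates". SAP 7.6.3 opens with a general rule that exploratory variables take the same analyses as the secondary ones.

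**The concern.** Two features sit badly together. First, the lead statistic needs half of an arm to have an event. The population has no cirrhosis at entry (Protocol 4.3 excludes "Presence of cirrhosis on liver biopsy (stage 4 fibrosis") and is followed for under two years, so an informative median is improbable. Second, the Protocol asks about the effect of EFX, and the section describes each arm separately.

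The omission is out of pattern. The next section, SAP 7.6.3.5, gives adjudicated cardiovascular events a CMH comparison, a difference in proportions with a Miettinen-Nurminen interval, an odds ratio and a risk ratio. Protocol 6.25.1 describes preventing progression to cirrhosis and its complications as a key objective, yet the endpoint that captures it has no specified effect estimate.

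At stake is whether the report contains a pre-specified estimate of that effect with an interval, or one chosen after the data are seen. A dating problem adds a second risk: a median could appear that reflects only a handful of subjects still at risk.

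**Working it through.** The documents state no EFS event count, hazard, median or power, so there is no planned figure to reproduce.

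**Inputs**
- 40 subjects per arm: Protocol 5.2.2, "Placebo QW (n = 40"), with the same number for each EFX dose. The totals in the sample-size section are redacted.
- Follow-up: Protocol 3.1, "subjects will transition into the long-term safety follow-up portion of the study and will be followed until Week 96". T = 96/52.18 = 1.84 years.
- Event rate: Protocol 7.13 refers to an assumed annual rate but gives no number. The rates below, 3% to 15% per year, are my assumption.
- Week 96 biopsy window: minus 8 to plus 4 weeks (Protocol Appendix B), so Weeks 88 to 100.

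**Event rate needed**
- Median by Week 96: annual risk = 1 − 0.50^(1/1.84) = 31% (hazard ln 2/1.84 = 0.377 per year).
- 25th percentile by Week 96: annual risk = 1 − 0.75^(1/1.84) = 14%.

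**Chance of enough events, ignoring censoring**

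Cumulative risk p = 1 − (1 − r)^1.84; events in an arm are binomial (40, p).

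| Annual risk r | p at Week 96 | Expected events | P(≥20 of 40) | P(≥10 of 40) |
|---|---|---|---|---|
| 3% | 5.4% | 2.2 | 3e-15 | 0.00004 |
| 5% | 9.0% | 3.6 | 3e-11 | 0.2% |
| 10% | 17.6% | 7.0 | 3e-6 | 15% |
| 15% | 25.8% | 10.3 | 0.0009 | 61% |

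Above that range, P(≥20 of 40) is 0.6% at 30% cumulative risk and 13% at 40%.

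**Censoring and the tail of the curve**

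Counting events is not the whole condition for a Kaplan-Meier median, because the risk set shrinks. Cirrhosis can be dated at a biopsy as late as Week 100. An event-free subject leaves at the last assessment, which might be the Week 96 visit or the 30-day follow-up. With the last dose at Week 95, that follow-up falls at about 95 + 30/7 = Week 99.3. Late events then fall on few remaining subjects.

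A simulation shows the size. It assumed 40 per arm, 25% dropout by Week 96, a quarter of events at the Week 24 biopsy, and the other events at biopsies spread evenly over Weeks 88 to 100. The share of arms whose curve reached 0.5, almost always after Week 96, was:

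| Cumulative risk | Censored at Week 96 | Censored at the later of biopsy and Week 99.3 |
|---|---|---|
| 5% | 32% | 5% |
| 10% | 53% | 10% |
| 20% | 78% | 21% |
| 30% | 89% | 31% |

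These medians are artefacts. They depend on the assumed dropout and timing, but they show that the censoring date matters.

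**What a contrast would give**
- Example: 91% versus 97% event-free, 40 per arm. SE = √(0.09×0.91/40 + 0.03×0.97/40) = 0.053, and 1.96 × 0.053 = 0.103, so about ±10 points. This is a Wald interval on 3.6 and 1.2 expected events. The 3% arm has a 0.97^40 = 30% chance of no events, where that approximation fails.
- Log-rank power at an assumed hazard ratio of 0.5, one EFX arm against placebo: Φ(½√d × |ln 0.5| − 1.96), with d events. Placebo 96-week risks of 5%, 10%, 20% and 30% give d of about 3, 6, 12 and 18 and power of 9%, 13%, 23% and 32%. For 80% power, 4 × (1.96 + 0.842)²/(ln 0.5)² = 65.3, so 66 events.

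**The case against.** The best defence is that EFS is exploratory, carries no decision or multiplicity role, and may reasonably be described rather than tested. Several parts of this stand.

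- **Counts are firm.** The number and percentage with an event will be given by treatment group, which meets the Protocol's reference to event rates. A reader might infer that the plan leaves the outcome question wholly unanswered; it does not. What is missing is an effect estimate with an interval, and an estimate by arm that accounts for unequal follow-up. The formal exploratory objective is redacted, so its exact wording cannot be judged.
- **An unreached median is foreseen.** The fallback is a sensible statistic. Its weakness is that it is optional and has no time points. It would also not be triggered if a spurious median appeared.
- **The general rule in SAP 7.6.3 might import CMH.** Having an event or not is binary, so one could read the rule as requiring a CMH comparison of event proportions. That reading is possible, so it would be too strong to say that no contrast can result. But 7.6.3.4 sets out its own method without a comparison, and no secondary analysis is time-to-event. The rule does not clearly settle the matter.
- **Few events limit any method.** This is right, and it is why a stratified log-rank test would add little. It favours an estimate with an interval over a test; it does not favour leaving the contrast out.

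**Conclusion.** The point holds as an inexpensive improvement to an exploratory analysis. With 40 per arm and 96 weeks, the lead statistic is very unlikely to be informative: P(≥20 of 40 events) is below 0.001 throughout an assumed 3% to 15% per year. No EFX-placebo estimate is named in the section.

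Two stronger readings are not supported. One is that the median will be inestimable in every arm. That depends on an event rate the documents do not give, and late biopsy dating could produce a median, though a misleading one. The other is that all the planned percentiles are useless: at 15% per year the 25th percentile would be reached in about 61% of arms.

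The conclusion rests on the assumed event rates, the 40 per arm in Protocol 5.2.2, and, for the tail artefact only, the simulation's dropout and biopsy timing.

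**What to change.** In SAP 7.6.3.4:

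1. Make the planned summary the Kaplan-Meier event-free probability with 95% CI, by arm, at Week 24, Week 48 and Week 100. Week 100 is used because a Week 96 cut would miss cirrhosis read on biopsies taken up to four weeks later.
2. Add the EFX-minus-placebo difference with 95% CI for each dose and for All EFX, using an interval method that behaves with few or zero events, and label it exploratory.
3. Define event and censoring dates so that event-free subjects with a Week 96 biopsy stay at risk to the end of the biopsy window.
4. Report the median only if it is reached with adequate numbers at risk, and show those numbers.
5. Leave out a stratified log-rank test; the expected events are too few for it to help.

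The cost is SAP wording and one table, with no new data. The downside is a wide interval, about ±10 points in the example above, which supports description and not a claim of effect.
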